2.1.3 Recruitment Strategies

This study will be listed on available websites (www.clinicaltrials.gov) and participants will be recruited from the current patient population at NIH and participating sites.

2.2 SCREENING EVALUATION

Note: Screening evaluation testing/procedures are conducted under the separate screening protocol, 01-C-0129 (Eligibility Screening and Tissue Procurement for the NIH Intramural Research Program Clinical Protocols).

1. The following tests may be obtained any time prior to enrollment:
 - Pathological confirmation of diagnosis and PSA expression in either the Laboratory of Pathology at NIH Clinical Center, Walter Reed National Military Medical Center at Bethesda. However, if no pathologic specimen is available, patients may enroll with a pathologist's report showing a histologic diagnosis of prostate cancer and a clinical course consistent with the disease.
2. The following parameters will be obtained within 8 weeks prior to enrollment:
 - HIV test
 - Hepatitis B and C
3. The following parameters will be obtained within 30 days prior to enrollment:
 - Tc-99 whole body scintigraphy
 - CT of chest/abdomen /pelvis (MRI may be substituted at investigator's discretion).
 - History and physical examination with ECOG
 - Serum PSA
 - Complete blood count plus differential and platelet count
 - Hepatic and Acute Care panels
 - Testosterone level

2.3 REGISTRATION PROCEDURES

Registration and status updates (e.g., when a participant is taken off protocol therapy and when a participant is taken off-study) will take place per CCR SOP ADCR-2, CCR Participant Registration & Status Updates found [here](#).

2.3.1 Treatment Assignment and Randomization/Stratification Procedures

Cohorts

Number	Name	Description
1	Prostate Cancer Patients	Patients with chemotherapy naïve metastatic castrate-resistant prostate cancer

Short Title: Enzalutamide Vaccine in mCRPC

Version Date: 03/29/2022

Arms

Number	Name	Description
1	A	Enzalutamide alone
2	B	Enzalutamide with PSA-TRICOM

Stratifications

Name	Distinct Options	Notes
Prior Immunotherapy	Yes No	

Randomization and Arm Assignment

Patients must be registered with Central Registration Information Services within 24 hours after signing the consent. All Patients on study will be directly assigned to cohort 1.

Patients in cohort 1 will be randomized within 24 hours after registration. Block randomization will be used to randomly assign patients in a 1:1 manner between arms A and B. Randomization will be stratified by prior immunotherapy used as cancer treatment.

For randomization, authorized staff should call [contact] between the hours of 8:30 a.m. and 5:00 p.m., Monday through Friday. A recorder is available during non-working hours.

2.4 BASELINE EVALUATION

The following parameters will be obtained within 16 days prior to start of treatment:

2.4.1 Clinical Evaluation

- History and physical examination
- ECOG performance status (see [APPENDIX A](#))
- Height, Weight
- Baseline electrocardiogram (EKG) on all patients, and appropriate cardiologic evaluation, as clinically indicated, to provide baseline function and identify any patients who should be monitored closely for cardiac risks associated with vaccinia vaccination

2.4.2 Laboratory studies

- Complete blood count plus differential and platelet count
- Acute care panel
- Hepatic panel
- Mineral panel
- LDH, CK, Uric Acid, Total Protein
- urinalysis
- Serum PSA
- Serum CEA level

Short Title: Enzalutamide Vaccine in mCRPC

Version Date: 03/29/2022

- Lymphocyte phenotyping CD4/CD8
- HLA class I expression (results will not be required prior to enrollment)

2.4.3 Leukapheresis

Optional for HLA-A2 positive patients.

3 STUDY IMPLEMENTATION

3.1 STUDY DESIGN

The study will randomize chemotherapy-naïve, mCRPC patients to either enzalutamide alone or enzalutamide with PSA-TRICOM.

Enzalutamide will be given at the standard dose of 160 mg daily [[5](#)].

PSA-TRICOM will be administered identical to the Phase III dosing with vaccine given week 1 (vaccinia-PSA-TRICOM, 2×10^8 infectious units subcutaneously) and then fowlpox-vaccine (1×10^9 infectious units subcutaneously) given in week 3, week 5 and then every 4 weeks through week 21 [[35](#)].

After completing 6 months of vaccine, fowlpox-vaccine (1×10^9 infectious units subcutaneously) will be administered every 3 months based on previous clinical trial experience with PSA-TRICOM [[17](#)].

[figure not shown]
Patients will be treated until radiographic progression on scans using Prostate Cancer Working Group Criteria [[23](#)] (Response Criteria in this protocol have incorporated the Response Criteria and are discussed in section [5.3](#)). Re-staging will be done every 3 months similar to the AFFIRM trial [[5](#)]. For patients who have stable disease beyond 2 years and a PSA less than 1.0 ng/ml, they can defer restaging scans, based on investigator discretion.

The primary endpoint of this trial will be TTP, with secondary endpoints including overall survival, and exploratory analysis evaluating immunologic responses to vaccine with enzalutamide and to enzalutamide alone.

Short Title: Enzalutamide Vaccine in mCRPC

Version Date: 03/29/2022

FOR THE FIRST 18 CYCLES OF TREATMENT:

BEYOND 18 CYCLES OF TREATMENT:

Beyond 18 cycles of treatment, cycle length will increase to 42 days. Patients will return for follow up every 6 weeks instead of every 4 weeks. For those patients beyond 18 cycles of treatment receiving the PROSTVAC vaccine, they will receive a dose every second cycle instead of every third cycle, however, the number of weeks between doses of vaccine will remain unchanged at 12 week intervals. (To allow for the transition between 4 and 6 week cycles, one dose of vaccine will be given at a 10 week interval). Similarly, for patients who have been on treatment more than 18 cycles, restaging scans will be every second cycle instead of every third cycle, however, the number of weeks between restaging scans will remain unchanged at 12 weeks intervals. For patients who have stable disease beyond 2 years and a PSA less than 1.0 ng/ml, they can defer restaging scans, based on investigator discretion.

3.2 ADMINISTRATION

Patients who have been treated for less than 18 cycles will receive enzalutamide 160mg orally, daily on days 1 – 28 in a 28-day cycle, and will continue this dosing throughout the cycle.

Patients who have been treated for more than 18 cycles will receive enzalutamide 160mg orally, daily on days 1 – 42 in a 42-day cycle, and will continue this dosing throughout the cycle. The study drug will be dispensed by the NIH Clinical Center Pharmacy.

Patients randomized to Arm B will receive vaccines at the NIH Clinical Center. The vaccines will be prepared and placed in syringes by the Clinical Center Pharmacy personnel at the NIH. Please see section 3.1 for dose, schedule and route of administration. Dosing and administration of PSA-TRICOM will be performed in the Day Hospital. Patients will be monitored with vital signs (blood pressure, heart rate, respiratory rate, temperature) prior to and within 1 hour after the initial vaccine treatment. Patient will be monitored with vital signs prior to subsequent vaccine treatments, and will remain in the Day Hospital for at least 30 minutes following

administration of vaccine for observation of adverse reactions. (Post-vaccine vital signs will not be required except for the first vaccination.)

3.3 DOSE MODIFICATIONS/DELAYS

3.3.1 Vaccine Dose Modification: None

3.3.2 Enzalutamide Dose Modification

If a patient experiences a \geq Grade 3 non-hematologic toxicity attributable to enzalutamide or an intolerable side effect attributable to enzalutamide, withhold dosing for one week or until symptoms improve to \leq Grade 2, then resume at the same dose if clinically appropriate.

Treatment may be held if clinically appropriate as determined by the investigator and may be restarted as long as patient has not demonstrated radiographic disease progression as defined in the protocol. If toxicity recurs and or in the judgment of the investigator dose reduction is appropriate, lower dose levels (120 mg /DL-1 or 80 mg/DL-2), may be considered.

3.3.2.1 Enzalutamide Dose Delay

If the planned enzalutamide dose is missed due to scheduling or logistical issues (e.g., vacation, weather) during a cycle or delay in starting a cycle, it may be started within 14 days of the appointed time.

3.3.3 Criteria for individual patient re-treatment

3.3.3.1 Patients with grade 3 non-autoimmune toxicity due to the treatment regimen, may resume treatment provided that the toxicity has decreased to baseline or grade 2 toxicity within 60 days from the last day of treatment. See section **3.6.1** Criteria for removal from protocol therapy.

3.3.3.2 Patients receiving vaccine with \geq grade 3 autoimmune toxicity will not be treated and will be removed from study.

3.3.3.3 Patients who develop any grade 4 toxicity attributable to protocol treatment will be removed from the protocol treatment and followed for resolution of toxicity

3.3.3.4 Patients who develop grade 3 injection site reactions will have their vaccine held until injection site reaction resolves to grade 2 or less.

3.3.3.5 If a scheduled vaccine dose is missed due to scheduling or logistical issues, the vaccine may be given within 14 days of the appointed time.

Short Title: Enzalutamide Vaccine in mCRPC

Version Date: 03/29/2022

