3.6 CRITERIA FOR REMOVAL FROM PROTOCOL THERAPY AND OFF STUDY CRITERIA

3.6.1 Criteria for removal from protocol therapy

- Disease progression as evidenced by radiographic or clinical progression (defined in section [5.3.5](#)).
- Intercurrent illness or medical circumstances: if at any time the constraints of this protocol are detrimental to the patient's health, the patient may be removed from protocol therapy. In this event, the reasons for withdrawal will be documented.
- Patient's request to be taken off study. In this event, the reasons for withdrawal will be documented.
- If patients are non-compliant with the protocol guidelines, they may be removed from the study at the discretion of the principal investigator.
- Any Grade 4 toxicity that is possibly, probably or definitely related to the protocol treatment will require a patient to be off-treatment.
- Grade ≥ 3 autoimmune toxicity while on vaccine, will require a patient to be off-treatment.
- Any Grade 3 non-autoimmune toxicity that does not resolve to Grade 1 or baseline within 60 days and is possibly, probably or definitely related to the protocol treatment will require a patient to be off-treatment.
- Any grade of seizure will require discontinuation of enzalutamide but patients may continue vaccine at the discretion of the investigator.

Prior to documenting removal from protocol therapy, effort must be made to have all subjects complete a safety visit approximately 30 days following the last dose of study therapy.

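### A man whose treatment-related grade 3 toxicity is still at grade 2 on day 60, above his baseline, may resume under 3.3.3.1 but must come off treatment under 3.6.1, and the protocol does not say which governs

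*Combined protocol and SAP*

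**What the plan says.** Two sections of the protocol govern the same kind of event.

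- Section 3.3.3.1 (re-treatment) applies to "Patients with grade 3 non-autoimmune toxicity due to the treatment regimen". Such men "may resume treatment provided that the toxicity has decreased to baseline or grade 2 toxicity within 60 days from the last day of treatment". It then refers the reader to 3.6.1, by its title, "Criteria for removal from protocol therapy".
- Section 3.6.1 (removal) lists "Any Grade 3 non-autoimmune toxicity that does not resolve to Grade 1 or baseline within 60 days". It adds a condition of relatedness at any of three degrees, and the item ends "definitely related to the protocol treatment will require a patient to be off-treatment".

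Two neighbouring sections bear on the same question. Section 3.3.2 has enzalutamide withheld for a grade 3 or higher non-hematologic toxicity attributed to it, for one week or until improvement to grade 2 or lower, "then resume at the same dose if clinically appropriate". It adds that held treatment "may be restarted as long as patient has not demonstrated radiographic disease progression". Section 3.3.3.4 says that men with grade 3 injection-site reactions "will have their vaccine held until injection site reaction resolves to grade 2 or less". Neither gives an outer time limit or mentions 3.6.1.

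Under 3.6.2, a man who is off treatment and has had a visit at about 30 days, where feasible, is off study. Section 5.3.7 defines time to progression (TTP) from start of treatment to progression and gives no censoring rule.

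**The concern.** One rule is a permission to re-dose and the other a mandatory stop, and they set different recovery grades for the same event over the same number of days. Site staff could follow either section in good faith and breach the other. The deviation reporting in section 7.8 then has no fixed rule to measure against.

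The first thing at stake is consistent safety handling. There is a possible second consequence for the primary endpoint. Treatment status leads to study status through 3.6.2, and restaging is scheduled for men on study. Whether such a man's progression is observed may therefore depend on which section was applied to him.

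**Working it through.** **Step 1. The two rules side by side.**

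| Element | 3.3.3.1 | 3.6.1 |
|---|---|---|
| Event | grade 3, non-autoimmune, due to the regimen | grade 3, non-autoimmune, related at any of three degrees |
| Recovery level | baseline or grade 2 | baseline or grade 1 |
| Window | 60 days | 60 days |
| Start of window | last day of treatment | not stated |
| Force | may resume | off treatment required |

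The relatedness wording differs, but an event due to the regimen falls under both.

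**Step 2. Where they collide.** I read the recovery level in 3.3.3.1 as grade 2 or lower.

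| State at day 60 | 3.3.3.1 | 3.6.1 | Conflict |
|---|---|---|---|
| Grade 1 or lower | may resume | no removal | no |
| Grade 2, baseline grade 2 | may resume | no removal | no |
| Grade 2, baseline below grade 2 | may resume | off treatment | yes |
| Still grade 3 | may not resume | off treatment | no |

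The contradiction occupies one cell.

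**Step 3. Does the cross-reference settle it?** It names 3.6.1 but states no order of precedence. The clocks do not help either. For a man who reaches grade 2 early and resumes, the protocol does not say whether the 60 days of 3.6.1 run from onset, from the dose before the hold, or from some later date.

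**Step 4. The plan's own design figure.** Inputs from section 9: one-sided alpha 0.10, power 80%, hazard ratio 1.80 (hazards 0.0693 and 0.0385), 36 men per arm, 36 months of accrual, 48 months in total, 52 events. Section 9 gives the medians of 10 and 18 in cycles after stating 10 months; I used months.

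- Events required (Schoenfeld): 4 × (1.2816 + 0.8416)² / (ln 1.80)² = 4 × 4.508 / 0.3455 = 52.19. The plan's 52 is reproduced.
- Power at d events: Φ(√d × ln 1.80 / 2 − 1.2816). At d = 52 this is Φ(7.211 × 0.2939 − 1.2816) = Φ(0.838) = 79.9%, against the stated 80%.
- Expected events per arm: 36 × [1 − (e^(−12λ) − e^(−48λ)) / (36λ)]. This gives 30.2 + 23.7 = 54.0 (53.97 before rounding), consistent with 52.

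**Step 5. Size, by assumption only.** The documents give no rate of grade 3 toxicity that stays at grade 2, so the number of lost events is a range, not an estimate.

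| Events observed | 52 | 51 | 50 | 49 | 48 | 47 | 46 |
|---|---|---|---|---|---|---|---|
| Power | 79.9% | 79.3% | 78.7% | 78.1% | 77.5% | 76.8% | 76.2% |

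A simulation of the design (20,000 runs per scenario) censored men during their first 12 months, independently of prognosis. Power was 80.5% with no removals, and 79.3%, 79.2% and 77.5% with 2, 3 and 5 men censored per arm. Censoring 2 or 5 men in Arm B only gave 80.0% or 79.1%, with one-sided type I error still about 0.10.

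**The case against.** The strongest defence is that the rules can be read in sequence: a man may resume at grade 2, and 3.6.1 then takes him off if grade 1 or baseline has not been reached by day 60. The permissive wording of 3.3.3.1 and its pointer to 3.6.1 fit that reading. It narrows the conflict but does not remove it, because the protocol states neither the sequence nor the start of the 60 days in 3.6.1.

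Several stronger readings are tempting, and the documents do not support them.

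- *That 3.3.3.4 and 3.3.2 are further contradictory rules.* Both are silent on an outer time limit, and silence can be read as subject to 3.6.1. Agent-specific rules may also be deliberate: 3.6.1 itself separates the two products for seizure.
- *That many men are affected.* Section 13.4.6.2 reports grade 3 or higher reactions in 47% of enzalutamide patients, but also in 53% on placebo. It gives no basis for a large pool of related events.
- *That the conflict biases the comparison because only Arm B receives vaccine.* Section 1.2.3 describes common injection-site reactions as grade 1. Unequal censoring would bias the test only if it were related to prognosis, and nothing in the documents shows that.
- *That TTP is censored at removal.* No section says so. It is inferred from 3.6.2 and the silence of 5.3.7, and that gap affects every removal without progression. Aligning the two grades would not close it.

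**Conclusion.** The text is wrong as written. Sections 3.3.3.1 and 3.6.1 are both current and give opposite instructions for a man with a related grade 3 non-autoimmune toxicity that is still at grade 2 on day 60, when his baseline was below grade 2. This follows from the wording and rests on no number.

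The number of such men is unknown and probably small. Under the assumed losses above, power falls by at most about 4 points (79.9% to 76.2% at 6 lost events). No bias between arms has been shown. The link to TTP follow-up is plausible but inferred.

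It is a consistency correction, worth making because a stopping rule should not contradict itself, and it does not threaten the trial's conclusions. I take no view on which recovery grade is right.

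**What to change.** Reconcile 3.3.3.1 with 3.6.1. The amended text should say which section governs and on what date the 60 days begin. It should also confirm how 3.3.2 and 3.3.3.4 relate to 3.6.1. The recovery grade is for the sponsor's clinical team to settle, and these sections need not share one agent-independent rule.

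Section 6.5.2 records that the study had closed to accrual by 12/20/2016, so an amendment to this March 2022 version reaches only men still on treatment. For those already handled, list by arm who resumed and who was removed with residual grade 2 toxicity, with the date each left study. The TTP report can then show how many outcomes rest on the conflict.

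The cost is a few lines of amendment and one short listing.

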3.4 STUDY CALENDAR

Short Title: Enzalutamide Vaccine in mCRPC

Version Date: 03/29/2022

	Screening and Baseline	Treatment 1 cycle = 28 days; C=Cycle; D=Day												
		D -56 to D1	C1 D1	C1 D15	C2 D1	C3 D1	C4 D1	C5 D1	C6 D1	C7 D1	C8 D1	C9 D1	C10+ D1 ¹³	End of Study
Hep B/HepC, HIV	X ⁷													
Lymphocyte Phenotyping TBNK ¹²	X			X	X	X	X	X	X	X	X	X ⁵	X	
HLA testing (results not required prior to enrollment)	X													
ECG	X ⁸													
Tc 99 scintigraphy ¹²	X ⁸					X			X			X ⁹		
CT-C/A/P, or MRI ¹²	X ⁸					X			X			X ⁹		
Immunology Assays ^{10, 12}	X			X		X								
Adverse Events		X											→	
Concomitant Medications	X			→										

Footnotes:

¹ For patients in Arms A and B

² Cycle length will increase from 28 days to 42 days at cycle 19 day 1. Enzalutamide 160mg p.o. daily will be given every 28 days/ cycle until cycle 19 day 1 and then every 42 days/cycle thereafter. For patients who have had stable disease beyond 2 years and no SAEs related to the treatment, patients may be followed up in clinic at intervals of 12 weeks (consistent with clinical practice.) Vaccine dosing may be adjusted to accommodate the new schedule as long as it is not given at less than a 28-day interval.

³ Only for patients randomized to Arm B (Enzalutamide + Vaccine).

⁴ rF-PSA-TRICOM, will be given every 12 weeks after cycle 6 day 1 (To allow for the transition between 4 and 6 week cycles at cycle 19, one dose of vaccine will be given at a 10 week interval).

⁵ HPE, ECOG, CBC, Chem, PSA, and Lymphocyte Phenotyping will be obtained every cycle.

Short Title: Enzalutamide Vaccine in mCRPC

Version Date: 03/29/2022

⁶ Pathologic confirmation will be obtained any time prior to enrollment.

⁷ HepB/HepC/HIV status will be obtained within 8 weeks prior to enrollment.

⁸ Baseline ECG, Tc99 scintigraphy and CT-CAP or MRI will be obtained within 30 days prior to enrollment.

⁹ Restaging will be done every 12 weeks or earlier if clinically indicated. For patients who are on-study beyond 24 months who do not have a rising PSA, CT and bone scan can be deferred based on clinical judgement of the investigator.

¹⁰ After C4D1, samples may be collected prior to treatment at C13, C19, then every 6 months at restaging while on-study.

¹¹ As indicated in section **11.3**, all subjects will be offered the opportunity to complete an NIH Advance Directives form. This should be done preferably at baseline but can be done at any time during the study as long as the capacity to do so is retained. The completion of the form is strongly recommended, but is not required.

¹² Blood work and restaging scans may be obtained +/- 7 days of clinic visit/assessment for logistical and scheduling purposes.

¹³ Due to the Covid-19 pandemic, subjects with long term stable disease (>3) may have virtual visits and blood work performed with local provider

3.5 COST AND COMPENSATION

3.5.1 Costs

NIH does not bill health insurance companies or participants for any research or related clinical care that participants receive at the NIH Clinical Center. If some tests and procedures performed outside the NIH Clinical Center, participants may have to pay for these costs if they are not covered by insurance company. Medicines that are not part of the study treatment will not generally be provided or paid for by the NIH Clinical Center.

3.5.2 Compensation

Participants will not be compensated on this study.

3.5.3 Reimbursement

The NCI will cover the costs of some expenses associated with protocol participation. Some of these costs may be paid directly by the NIH and some may be reimbursed to the participant/guardian as appropriate. The amount and form of these payments are determined by the NCI Travel and Lodging Reimbursement Policy.

3.6 CRITERIA FOR REMOVAL FROM PROTOCOL THERAPY AND OFF STUDY CRITERIA

3.6.1 Criteria for removal from protocol therapy

- Disease progression as evidenced by radiographic or clinical progression (defined in section [5.3.5](#)).
- Intercurrent illness or medical circumstances: if at any time the constraints of this protocol are detrimental to the patient's health, the patient may be removed from protocol therapy. In this event, the reasons for withdrawal will be documented.
- Patient's request to be taken off study. In this event, the reasons for withdrawal will be documented.
- If patients are non-compliant with the protocol guidelines, they may be removed from the study at the discretion of the principal investigator.
- Any Grade 4 toxicity that is possibly, probably or definitely related to the protocol treatment will require a patient to be off-treatment.
- Grade ≥ 3 autoimmune toxicity while on vaccine, will require a patient to be off-treatment.
- Any Grade 3 non-autoimmune toxicity that does not resolve to Grade 1 or baseline within 60 days and is possibly, probably or definitely related to the protocol treatment will require a patient to be off-treatment.
- Any grade of seizure will require discontinuation of enzalutamide but patients may continue vaccine at the discretion of the investigator.

Prior to documenting removal from protocol therapy, effort must be made to have all subjects complete a safety visit approximately 30 days following the last dose of study therapy.

